6.1.2.6 PSA Undetectable Level

The undetectable level of PSA is defined as a level $< 0.2 \text{ ng/mL}$.

For patients with a detectable level of PSA at baseline, a dichotomous variable (‘Y’/‘N’) is derived to assign ‘Y’ to patients with any post-baseline PSA sample results $< 0.2 \text{ ng/mL}$. otherwise ‘N’ is assigned. For patients with undetectable level of PSA at baseline, this variable is kept missing.

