#### Secondary Endpoints

- *rPFS:* Defined as the time from randomization to the first objective evidence of radiographic disease progression as assessed by the investigator or death (defined as death from any cause within 24 weeks from study drug discontinuation), whichever occurs first.
- *Time to first SSE:* Defined as the time from randomization to the occurrence of the first SSE. SSE is defined as radiation or surgery to bone, clinically apparent pathological bone fracture or spinal cord compression.

- CONFIDENTIAL -

- *Time to castration resistance:* Defined as the time from randomization to the first castration-resistant event (radiographic disease progression, PSA progression or SSE), whichever occurs first.
- *PSA Response  $\geq 50\%$ , PSA Response  $\geq 90\%$ :* is defined as  $\geq 50\%$  and  $\geq 90\%$  reductions in PSA level from baseline to the lowest post-baseline PSA result as determined by the central laboratory, with a consecutive assessment conducted at least 3 weeks later to confirm the PSA response, respectively. The serum PSA response rate will be summarized at each time point. Waterfall plots of the rate of change from baseline will be constructed. PSA response  $\geq 50\%$  and  $\geq 90\%$  will be calculated by treatment group for subjects with PSA values at the baseline assessment and at least 1 post-baseline assessment.
- *Time to initiation of a new antineoplastic therapy:* Defined as the time from randomization to the initiation of antineoplastic subsequent to the study treatments.
- *PSA undetectable rate:* Defined as percentage of subjects with detectable ( $\geq 0.2$  ng/mL) PSA at baseline which become undetectable ( $< 0.2$  ng/mL) during study treatment.
- *ORR:* Defined as the percentage of subjects with measurable disease at baseline who achieved a complete or partial response in their soft tissue disease using the RECIST version 1.1 criteria on CT/MRI, and for bone lesions on bone scans.

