**Table 1 Schedule of Assessments**

Study Day	Screening Visit ¶¶¶	1 #	29	57	85 and Every Subsequent 28 Days	Safety Follow-up	Unscheduled Visit †	Long Term Follow-up ‡	
								Post Treatment Follow-up	Survival Follow-up
Study Week	-4 to -1 (28 Days)	1	5	9	13 and Every Subsequent 4 Weeks	30 Days after Last Dose §	Every 12 Weeks	Every 12 Weeks	
Window (Days)			± 3	± 3	± 3	± 7	NA	± 7	± 7
Informed Consent	X								
Medical History	X								
Inclusion/Exclusion Criteria	X	X							
Randomization (IRT)		X							
Vital Signs	X	X	X	X	X	X	X		
Physical Examination including Weight ¶	X	X	X	X	X	X	X		
Height	X								
12-lead ECG	X	X				X			
Clinical Labs ††	X	X	X	X	X	X	X		
PSA ‡‡	X	X	X	X	X	X		X	
Testosterone ‡‡					X ¶¶¶¶			X	
CT/MRI and Bone Scan §§, ¶¶	X §§				X ¶¶¶¶			X	
Chest X-ray or Chest CT/MRI †††	X				X ¶¶¶¶			X	
ECOG Performance Status	X	X	X		X ¶¶¶¶	X	X		
QoL Assessment (QLQ-PR25, EQ-5D-5L, FACT-P, Brief Pain Inventory-Short Form)		X			X ¶¶¶¶	X		X ‡	X ‡
Adverse Events ¶¶¶¶	X	X	X	X	X	X	X	X ¶¶¶¶	
Previous and Concomitant Medications	X	X	X	X	X	X	X		
Study Drug Dispensing		X	X	X	X				
Study Drug Treatment		X	X	X	X				

CT: computed tomography; ECG: electrocardiogram; ECOG: Eastern Cooperative Oncology Group; EQ-5D-5L: EuroQol Group-5 Dimension-5 Level Instrument;

IRT: Interactive Response Technology; MRI: magnetic resonance imaging; NA: not applicable; PSA: prostate-specific antigen;

FACT-P: Functional Assessment of Cancer Therapy-Prostate; QLQ-PR25: Quality of Life Prostate-specific Questionnaire; QoL: quality of life

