- ‡ After treatment discontinuation, all subjects MUST undergo long-term follow-up. Long-term follow-up assessments will be composed of post-treatment follow-up and survival follow-up. For those subjects who discontinue study treatment without radiographic disease progression confirmed will undergo post-treatment follow-up (calculated from baseline), include monitoring for survival status, disease progression, new antineoplastic therapies for prostate cancer and symptomatic skeletal events. Subjects will continue to be scanned along with collecting PSA and testosterone every 12 weeks until radiographic progression is confirmed by investigator assessment or the required number of PSA progression events for the final analysis is reached. For those subjects who discontinue study treatment due to confirmed radiographic disease progression will undergo survival follow-up (calculated from date of progression), include monitoring for survival status, new antineoplastic therapies for prostate cancer and symptomatic skeletal events, and the follow-up may be conducted by telephone interview. If seen in clinic, QoL assessment will also be completed until the initiation of new antineoplastic therapy for prostate cancer or the required number of PSA progression events for the final analysis is reached. Additional follow-up contacts may be requested.
- § Or prior to initiation of another investigator agent or new antineoplastic therapy for prostate cancer, whichever occurs first.
- ¶ A brief physical examination is required at each visit, with the exception of the screening visit during which a complete physical examination will be completed.
- †† Laboratory assessments include serum chemistries and hematology.
- ††† For subjects who discontinue study treatment without confirmed radiographic progression, subjects will continue to be collected PSA and testosterone every 12 weeks until radiographic progression is confirmed or the required number of PSA progression events for the final analysis is reached.
- §§ The abdominal-pelvic contrast CT scan or MRI, bone scan, chest x-ray or chest contrast CT must occur within 6 weeks of day 1; otherwise the screening visit assessment must be repeated. Radiographic assessments performed prior to informed consent, as part of the routine care, may be used as the baseline assessment if performed within 6 weeks of day 1 and if digital format images are available for submission to the sponsor.

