## **5.3 Efficacy Assessment**

### **5.3.1 Efficacy Assessment**

#### **5.3.1.1 PSA**

Blood samples for PSA will be collected at each scheduled visit during study treatment and at the safety follow-up visit. All samples will be analyzed by sponsor designated central laboratory.

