**PSA undetectable rate:**

The undetectable level of PSA is defined as  $< 0.2$  ng/mL. The PSA undetectable rate is defined as the percentage of subjects with detectable ( $\geq 0.2$  ng/mL) PSA at baseline, which becomes undetectable ( $< 0.2$  ng/mL) during study treatment and will be summarized at each time point. Only subjects with detectable PSA at baseline will be included in this analysis.

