- ‡‡ For subjects who discontinue study treatment without confirmed radiographic progression, subjects will continue to be collected PSA and testosterone every 12 weeks until radiographic progression is confirmed or the number of PSA events is reached.
- §§ The abdominal-pelvic contrast CT scan or MRI, bone scan, chest x-ray or chest contrast CT must occur within 6 weeks of day 1; otherwise the screening visit assessment must be repeated. Radiographic assessments performed prior to informed consent, as part of the routine care, may be used as the baseline assessment if performed within 6 weeks of day 1 and if digital format images are available for submission to the sponsor.
- ¶¶ The window for all radiological (CT/MRI) assessments is ± 7 days. For subjects who discontinue study treatment without radiographic progression, subjects will continue to be scanned every 12 weeks until radiographic progression is confirmed or the number of PSA events is reached.
- ††† Chest contrast CT or chest MRI is required at all imaging time points if screening chest x-ray demonstrates metastatic chest disease.
- §§§ Adverse events will be collected from the time the subject signs the consent form until the end of the safety reporting period (or until screen failure). The safety reporting period ends at the time of the safety follow-up visit, 30 days after last dose of study drug or initiation of another investigator agent or new antineoplastic therapy for prostate cancer.
- ‡‡‡ Testosterone, CT/MRI and Bone Scan, Chest X-ray or Chest CT or MRI, QoL Assessment and ECOG Performance Status will only be performed at day 85 and every subsequent 84 days (13 and every subsequent 12 weeks).
- ¶¶¶ The Screening period is 28 days. Re-screening may be allowed once and upon discussion with the medical monitor.

Table 2 Open-Label Phase Schedule of Assessments

Study Period or Visit	OL Screening	OL Treatment			Unscheduled Visit	OL Safety Follow-up	OL Long Term Follow-up
Study Week	NA	OL 1 (Day 1)	OL 5 (Day 29)	OL 13 and Every Subsequent 12 Weeks (Day 85 and Every Subsequent 84 Days)	Varies ¹	30 Days after Last Dose ²	Every 12 Weeks
Window (Days)	NA	NA	± 3	± 5	NA	± 7	± 7
Informed Consent ³	X						
Inclusion/Exclusion Criteria	X						
Open-Label Enrollment		X					
Brief Physical Examination		X		X	X	X	
Vital Signs including Weight		X	X	X	X	X	
ECOG Performance Status		X	X	X	X	X	
12-lead Electrocardiogram		X				X	
Clinical Labs ⁴		X	X	X	X	X	
Adverse Events ⁵		X	X	X	X	X	

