7.4.2.6 PSA Undetectable Rate

The PSA undetectable rate (also referred as the rate of PSA decline to <0.2 ng/mL) is defined as the percentage of patients with detectable (≥ 0.2 ng/mL) PSA at baseline, which becomes undetectable (< 0.2 ng/mL) during study drug.

In patients of the ITT population with detectable PSA at baseline, the PSA undetectable rates in enzalutamide+ADT and placebo+ADT will be compared by use of the stratified Cochran-Mantel-Haenszel score test.

The SAS code used to implement the Cochran-Mantel-Haenszel score test will be the same as PSA Response $\geq 50\%$ and PSA Response $\geq 90\%$ in Section 7.4.2.4.

In addition to providing the planned 95% CI for PSA undetectable rate (using the Clopper-Pearson method based on the exact binomial distribution), the difference in response rates between the treatment groups was summarized along with the 95% CI based on the asymptotic distribution.

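### SAP 6.1.2.6 scores PSA undetectable on any post-baseline sample, whereas SAP 7.4.2.6 and the protocol count only values reached on study treatment

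*SAP*

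**What the plan says.** - SAP 6.1.2.6 (derivation): among subjects with detectable baseline PSA, Y goes to "patients with any post-baseline PSA sample results" below 0.2 ng/mL, and N to the rest. The section mentions neither end of treatment, nor follow-up, nor new therapy, and it asks for no confirmatory value.
- SAP 7.4.2.6 (analysis): the rate is the percentage with detectable baseline PSA "which becomes undetectable (< 0.2 ng/mL) during study drug".
- Protocol 7.4.2: the change to undetectable must occur "during study treatment and will be summarized at each time point".
- Protocol synopsis: the same definition, ending "ng/mL) during study treatment".
- Protocol 5.3.1.1: "Blood samples for PSA will be collected at each scheduled visit during study treatment and at the safety follow-up visit". Protocol Table 1 places that visit "30 Days after Last Dose", with a window of 7 days either side, or earlier if a new therapy is about to start.
- Protocol Table 1, long-term follow-up footnote, for subjects who stop without confirmed radiographic progression: "Subjects will continue to be scanned along with collecting PSA and testosterone every 12 weeks until radiographic progression is confirmed". The SAP's copy of the schedule agrees: "subjects will continue to be collected PSA and testosterone every 12 weeks".

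**The concern.** The derivation rule is wider than the endpoint it is meant to derive. If every PSA sample were taken on study drug, the difference would be one of wording only. They are not, so a programmer working from 6.1.2.6 and one working from 7.4.2.6 could classify the same subject differently. Because no confirmation is required, one late value is enough to turn N into Y. The rate reported for a named secondary endpoint could then depart from the protocol definition, and some of it could reflect treatment received after study drug was stopped.

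**Working it through.** The plan states no figure to reproduce on this point. The check is a comparison of texts, followed by the weight of one subject.

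**1. Is there an off-drug sample for the two rules to disagree about?** Yes, from two sources.
- Safety follow-up visit. On schedule it falls 30 − 7 = 23 to 30 + 7 = 37 days after last dose. It is brought forward if a new therapy is to start, so it should not itself be a value on later therapy.
- Twelve-weekly post-treatment follow-up. By the Table 1 footnote, PSA collection there ends at confirmed radiographic progression or when the event target is met. It does not end at new therapy, which the same follow-up records. Sensitivity analysis TTPP_2 (SAP 6.1.1.2) deliberately uses PSA taken after new therapy starts, so the SAP itself expects such values.

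**2. Does another rule close the window in 6.1.2.6?**
- The opening of SAP 6.1.2 limits secondary variables only by the data cut-off date.
- SAP 6.1.2.4 (PSA response) drops samples taken after new antineoplastic therapy, but only for that section.
- SAP 6.1.2.7 confines best response to the treatment period and to the time before other therapy. Section 6.1.2.6 has no such clause.
- SAP 7.4 confines primary and secondary efficacy to the double-blind treatment period. It allows stated exceptions, and it defines the period by who is blinded, not by last dose.
- SAP Table 8 closes the last on-treatment window 3 days after last dose and places long-term follow-up after the double-blind period. SAP 7.12.3 introduces those windows for tables by visit. The 6.1.2.6 flag is one value per subject across all visits.

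**3. Does SAP 7.4 work as an on-drug limit elsewhere?** No. TTPP_1-1 (SAP 6.1.1.2 and Appendix 1) censors at the last PSA before treatment discontinuation and is presented as a change from the primary censoring rules. The primary TTPP analysis, which also falls under 7.4, can therefore use PSA drawn after discontinuation.

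**4. Who can be reclassified?** Only a subject with detectable baseline PSA who was never below 0.2 ng/mL on study drug and then has such a value off drug. Every subject scored Y on treatment is also Y under the literal rule, and the denominator is the same. Within an arm the literal rule can therefore only raise the rate or leave it unchanged. Its effect on the difference between arms can go either way.

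**5. Weight of one subject.** Planned arms are 120 and 60 (SAP section 4). Assume that all have detectable baseline PSA.
- Placebo: 100 × 1/60 = 1.67, about 1.7 points.
- Enzalutamide: 100 × 1/120 = 0.83, about 0.8 points.

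If fewer have detectable PSA at baseline, which is possible because limited prior ADT is allowed (Protocol 3.3), each subject weighs more.

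**The case against.** The best defence is that the two SAP sections do different jobs. Section 6.1.2.6 builds a Y/N variable, and 7.4.2.6 defines the quantity compared and carries the protocol's limit. Section 7.4 adds a general restriction to the double-blind period, and Table 8 puts long-term follow-up outside that period. Read together, they point to an on-treatment value. That reading is reasonable and probably what was meant, and it lowers the risk. It does not settle the matter: no rule says that section 7 prevails over section 6, 7.4 gives way to stated exceptions, and the primary endpoint shows that 7.4 is not applied as a last-dose limit.

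The defence is also right that the affected group is narrow. Subjects who stop for confirmed radiographic progression move to survival follow-up, for which the protocol footnote lists no PSA.

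Three stronger readings are tempting, and the documents do not support them.
- A reader might infer that open-label enzalutamide could inflate the placebo rate. SAP 7.5.2 says PSA is not assessed in the open-label phase, and Protocol Table 1 says subjects entering that phase do not enter long-term follow-up.
- A reader might infer that the documents already require a cut at 3 days after last dose. Neither SAP 7.4.2.6 nor the protocol says so. Protocol 6.1 permits interruptions of up to 14 consecutive days, so a subject who interrupts, gives a scheduled sample and then stops for good could lose a sample that arguably counts. A different convention, treatment plus 30 days, appears in Protocol 7.5 and SAP 6.2, although for adverse events. Under it, a safety-visit sample up to day 30 would count.
- A reader might infer a known bias towards one arm. The documents give neither the number of late first undetectable values nor their split by arm.

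**Conclusion.** The contradiction is real, and 6.1.2.6 is wrong as written: taken literally, it derives something other than the protocol's endpoint. Confidence is high on the texts and on the existence of off-drug samples. The size is unknown. The per-subject weights in step 5 rest on the planned arm sizes and on universal detectable baseline PSA, and they say nothing about how many subjects are involved. SAP 7.1 states that p-values for endpoints other than the primary are to be read descriptively, so the TTPP result and the type I error are unaffected. Severity is minor.

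**What to change.** In SAP 6.1.2.6, assign Y only when a post-baseline PSA below 0.2 ng/mL comes from a sample taken during study treatment, in line with SAP 7.4.2.6 and the protocol. State that long-term follow-up samples and samples after the start of new antineoplastic therapy do not count. The second exclusion is largely a safeguard, because starting a new prostate cancer therapy is already a reason to stop study drug (Protocol 6.1).

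The sponsor should also fix, before database lock, the last day after last dose that still counts as during study treatment, and say whether the safety follow-up sample falls inside it. The Table 8 boundary of 3 days is one option, not something the documents require. The choice should allow for samples taken in a permitted interruption.

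The cost is a sentence or two in the SAP and a date filter in the derivation. SAP section 1 allows revisions until hard lock.

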6.1.2.7 Overall Objective Response Assessment

The overall response assessment is based on RECIST version 1.1 for soft tissue lesion on CT/MRI, and for bone lesions on bone scans. The overall objective response is based on RECIST version 1.1 for soft tissue lesions.

The following categories were used:

- CR = complete response
- PR = partial response (option only for target lesions and overall)
- SD = stable disease (option only for target lesions and overall)
- PD = progressive disease
- Non CR/non PD= not complete response and not progressive disease (not an option for target lesions)
(option only for non-target lesions, bone lesions, and overall)
- Unconfirmed PD (not an option in RECIST on soft tissue lesions)
- NE = not evaluable (option for bone lesions)
= not evaluated/ not all evaluated (option for target and non target lesions)
= inevaluable (option for overall)
- NA = not applicable (postbaseline assessment in case of no lesion of the kind at baseline)
(not an option for overall response assessed by Investigator)

At each time point, the RECIST overall time point response, in patients with measurable soft tissue lesions at study entry (all patients, who have at least one target lesion), can be derived according to RECIST for all possible combinations of tumor response assessments in target and non-target lesions in soft tissues with or without the appearance of new unequivocal lesions. RECIST overall time point response derivation is described in Table 4. The RECIST overall time point response will be derived from the assessments provided by the investigators.

Investigator additionally considers image quality to perform their assessments.

For patients with no target and no non-target soft tissue lesion at baseline, the RECIST overall time point response is set to 'NA', unless an unequivocal new lesion is identified (in which case the assessment is PD) or unless imaging is not evaluable (in which case the assessment is NE).

Table 4 RECIST Overall Time Point Response for all Combinations of Tumor Responses in Target and Non-target Lesions with or without Appearance of new Lesions as assessed by Investigators

Target Lesions*	Non-Target Lesions*	Uequivocal New Lesions^	RECIST Overall Response^
CR	CR	No	CR
CR	Not applicable	No	CR
Not applicable	CR	No	CR
CR	Non-CR/Non-PD	No	PR
CR	Not evaluated	No	PR
PR	Not PD	No	PR
SD	Not PD	No	SD
PD	Any	Yes or No	PD
Any	PD	Yes or No	PD
Any	Any	Yes	PD
Not applicable	Non-CR/Non-PD	No	Non-CR/Non-PD
Not applicable	Not applicable	No	Not applicable \$
Not applicable	Not evaluated or Not Done	No	NE
Not evaluated or Scan not Done	Not PD	No	NE

* The category “Any” includes all possible categories (incl. NE or NA or Not Done). The category “Not PD” includes: CR, Non-CR/Non-PD, NA, NE and Not Done.

^ Missing assessments during study visits will not be imputed. Missing assessments for “Uequivocal new lesions” will be reported as “Missing” and will lead to “NE” for the derived RECIST Overall Response.

\$ The RECIST overall time point response will only be derived to “Not applicable” for patients with no target and no non-target soft tissue lesions at study entry in absence of new unequivocal lesion.

Definition of Best RECIST Overall Response

In patients with measurable soft tissue lesions at study entry (all patients, who have at least one target lesion), the best RECIST overall response in the soft tissue disease is the best of the RECIST overall time point response assessment reported at any time during or at the end of the treatment period, up to the start of any other antineoplastic prostate cancer therapy. The best RECIST overall response assessment is according to the following decreasing order, starting with the possible best response: CR, PR, SD, Non-CR/Non-PD, PD, NA, NE. For patients still on treatment after or by the cut-off date, the best RECIST overall response can be derived as the best of the RECIST overall time point response assessments recorded for the time on study up to the data cut-off date. Patients with no post-baseline assessment at any visit are reported in the ‘Not evaluated’ category.

The best RECIST overall response will be derived from the assessments provided by the investigators.

Definition of Best Overall Response

At each time point, the overall time point response assessment reported by the investigators are based on the combination of the time point assessments on soft tissue on target lesions, non-

target lesions and apparition of new lesions (i.e. RECIST), and the time point response assessment on bone scan.

The best overall response is the best of the overall time point response assessment reported at any time during or at the end of the treatment period, up to the start of any other prostate cancer therapy. The best of the overall time point response assessments is according to the following decreasing order, starting with the possible best response: CR, PR, SD, Non-CR/Non-PD, unconfirmed PD, PD, NA (for Investigator only), NE. For patients still on treatment after or by the cut-off date, the best overall response can be derived as the best of the overall time point response assessments recorded for the time on study up to the data cut-off date. Patients with no post-baseline assessment at any visit are reported in the 'Not evaluated' category.

The best overall response will be derived from the overall time point response assessments provided by the investigators.

Table 5 describes the possible combinations of tumor response to report the overall timepoint response assessment.

Table 5 RECIST Combined Time Point Response Provided for any Combinations of Tumor Responses in Soft tissue Lesions and Bone Lesions

RECIST 1.1	Bone Scan	The Combined (i.e., Overall) Time Point Response	
CR	CR	CR	
CR	NA	CR	
NA	CR	CR	
CR	NON-CR/NON-PD	PR	
CR	PDu	PR	
PR	CR	Not NE = & not PD	PR
PR	NON-CR/NON-PD		PR
PR	PDu		PR
PR	NA		PR
SD	CR	Not NE = & not PD	SD
SD	NON-CR/NON-PD		SD
SD	PDu		SD
SD	NA		SD
PD	Any	PD	
Any	PD	PD	
NON-CR/NON-PD	CR	Not NE = & not PD	NON-CR/NON-PD
NON-CR/NON-PD	NON-CR/NON-PD		NON-CR/NON-PD
NON-CR/NON-PD	PDu		NON-CR/NON-PD
NON-CR/NON-PD	NA		NON-CR/NON-PD
NA	NON-CR/NON-PD	NON-CR/NON-PD	
NA	PDu	PDu	
Any but PD	NE	NE	
NE	Any but PD	NE	
NA	Not applicable	NA	

PDu: unconfirmed Progression of Disease.

